STUDY PROTOCOL AND STATISTICAL ANALYSIS PLAN

Official Title:

Dynamic Magnesium Replacement Strategies and 28-Day Mortality in Non-Cardiac Critically Ill Patients: A Target Trial Emulation Study

Date: December 24, 2025

Principal Investigator: [name]., Ph.D.

Study Type: Observational (Retrospective Cohort)

SECTION 1: STUDY PROTOCOL

1. Study Identification

Brief Title:

Magnesium Replacement Strategies in Non-Cardiac ICU Patients

Official Title:

Dynamic Magnesium Replacement Strategies and 28-Day Mortality in Non-Cardiac Critically Ill Patients: A Nonrandomized Clinical Trial using Target Trial Emulation

Study Design:

Observational, Retrospective, Cohort Study.

2. Study Status

Overall Status: Completed (Retrospective analysis of existing data).

Study Start Date: September 2025 (Analysis start).

Primary Completion Date: December 2025.

Study Completion Date: December 2025.

3. Study Description

Brief Summary:

This study evaluates the association between different dynamic magnesium replacement strategies and 28-day all-cause mortality in non-cardiac critically ill patients with hypomagnesemia. Using data from the MIMIC-IV database, the study employs a target trial emulation framework (G-formula) to simulate and compare three strategies: 'Never Treat', 'Always Treat', and 'Dynamic Treat' (treat only when hypomagnesemic).

Detailed Description:

Magnesium supplementation is common in the ICU, but evidence for its mortality benefit in non-cardiac patients is lacking. This study aims to fill the gap by emulating a randomized controlled trial using observational data. We utilize the Medical Information Mart for Intensive Care IV (MIMIC-IV) database. We define 'Time Zero' as the first occurrence of hypomagnesemia (<1.7 mg/dL) within 72 hours of ICU admission. We apply the parametric G-formula to adjust for time-varying confounding affected by prior treatment, a method superior to conventional regression for dynamic treatment regimes. The study aims to inform clinical guidelines regarding the necessity and safety of routine magnesium repletion.

4. Study Design

Observational Model: Cohort.

Time Perspective: Retrospective.

Target Follow-Up Duration: 28 Days.

Biospecimen Retention: None.

5. Groups / Cohorts

Since this is a target trial emulation, the "Groups" are hypothetical strategies defined by the analysis as follows:

Group 1: Never Treat Strategy

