Description: A simulated strategy where patients receive no magnesium supplementation throughout the 28-day follow-up, regardless of serum magnesium levels.

Group 2: Always Treat Strategy

Description: A simulated strategy where patients receive daily magnesium supplementation throughout the 28-day follow-up.

Group 3: Dynamic Treat Strategy

Description: A simulated strategy where magnesium supplementation is administered on a given day only if the daily serum magnesium level falls below 1.7 mg/dL.

Reference: Natural Clinical Course (Observed data).

6. Eligibility Criteria

Study Population: Adult patients admitted to the ICU in the MIMIC-IV database (2008-2019).

Inclusion Criteria:

1. Age \geq 18 years.
2. Admitted to the Intensive Care Unit (ICU).
3. Developed hypomagnesemia (Serum Magnesium < 1.7 mg/dL) within the first 72 hours of ICU admission.

Exclusion Criteria:

1. Admitted due to cardiac or cardiosurgical causes (e.g., Cardiac Surgery Recovery Unit, CCU, CVICU).
2. Underwent cardiac surgery during hospitalization (identified by ICD-9/10 procedure codes).
3. Primary discharge diagnosis of major cardiac conditions (e.g., myocardial infarction, heart failure, arrhythmias).

7. Outcome Measures

Primary Outcome Measure:

1. 28-Day All-Cause Mortality

Description: Cumulative incidence of death from any cause within 28 days from inclusion (Time Zero).

Time Frame: 28 days.

Secondary Outcome Measures:

1. Risk Difference (RD)

Description: The absolute difference in mortality risk between the emulated strategies (Never/Always/Dynamic) and the natural clinical course or between strategies.

Time Frame: 28 days.

2. Number Needed to Treat (NNT)

Description: Calculated to estimate the number of patients needed to be managed under a specific strategy to avert one death.

Time Frame: 28 days.

SECTION 2: STATISTICAL ANALYSIS PLAN (SAP)

1. Analysis Dataset

Source: MIMIC-IV database (version 3.1).

Data Structure: Longitudinal dataset with a daily time-grid (days 0 to 27) relative to Time Zero (T0).

Missing Data Handling: Last Observation Carried Forward (LOCF) will be used for time-varying covariates.

2. Variables

Exposure (Treatment): Magnesium replacement therapy (binary variable per day: administered yes/no).

Baseline Covariates: Age, Gender, Charlson Comorbidity Index (CCI).

Time-Varying Covariates (Daily):

Laboratory: Serum magnesium, Hemoglobin, Creatinine, Arterial pH.

Vitals/Scores: Mean Blood Pressure (MBP), SOFA score.

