Therapeutics: Vasopressor use (binary).

Outcome: Death (binary).

Competing Event: Live discharge from ICU.

3. Statistical Methodology: The G-Formula

To estimate the causal effect of dynamic magnesium strategies while accounting for time-varying confounding affected by prior treatment (feedback loops), the parametric G-formula will be employed.

Step 1: Parametric Modeling

Pooled parametric regression models will be fitted for:

- The outcome (Death).
- The competing event (Live discharge).
- Each time-varying covariate (Mg, Hb, Cr, pH, MBP, SOFA, Vasopressors).

Model Specifications: Models will include lagged values, cumulative averages, and non-linear quadratic terms for continuous variables to capture complex dependencies. An interaction term between Magnesium Treatment and SOFA score will be included.

Step 2: Monte Carlo Simulation

A random sample of 5,000 subjects (bootstrapped) will be used for simulation.

We will simulate the 28-day trajectory of the cohort under the three specific interventions (Never Treat, Always Treat, Dynamic Treat) by setting the treatment variable according to the rule of each strategy and predicting subsequent covariates and outcomes based on the fitted models.

Step 3: Effect Estimation

Cumulative Risk: Calculated for mortality at Day 28 for each strategy.

Comparisons: Risk Difference (RD) and Risk Ratio (RR) will be calculated comparing 'Always Treat' and 'Dynamic Treat' against 'Never Treat' (Reference).

Inference: 95% Confidence Intervals (CIs) will be derived using non-parametric bootstrapping with 1,000 resamples.

4. Sensitivity Analyses

To verify the robustness of the G-formula models, the following analyses will be performed:

1. Simplified Models: Re-running the analysis using linear models for all covariates (excluding quadratic terms).
2. No Interaction Models: Re-running the analysis excluding the treatment-by-SOFA score interaction term.
3. E-value Calculation: To assess the potential impact of unmeasured confounding on the observed Risk Ratio.

5. Subgroup Analyses

Treatment effects will be evaluated across the following baseline subgroups:

1. Hypomagnesemia Severity: Severe vs. Mild (dichotomized by median).
2. Renal Function: Creatinine ≥ 1.2 vs. < 1.2 mg/dL.
3. Hemodynamic Status: Vasopressor use vs. None.
4. SOFA Score: ≥ 8 vs. < 8 .
5. Age: ≥ 65 vs. < 65 years.

Interaction p-values between subgroups will be estimated via bootstrap-based covariance correction.

6. Software

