All analyses will be performed using R (version 4.3.1) and the 'gfoRmula' package. A two-sided p-value < 0.05 will be considered statistically significant.

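### The 'Severe vs. Mild' magnesium subgroup is a sample-median split with no severity threshold behind it: it is coarse, and its label claims more than it can show

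*Combined protocol and SAP*

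**What the plan says.** Protocol section 6 makes a low magnesium value a condition of entry: "Developed hypomagnesemia (Serum Magnesium < 1.7 mg/dL) within the first 72 hours of ICU admission". The Detailed Description in Protocol section 3 ties the start of follow-up to the same value: "We define 'Time Zero' as the first occurrence of hypomagnesemia (<1.7 mg/dL) within 72 hours of ICU admission".

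SAP section 5 opens with "Treatment effects will be evaluated across the following baseline subgroups", and its first item is "Hypomagnesemia Severity: Severe vs. Mild (dichotomized by median". The item gives no mg/dL value, no rule for patients exactly at the median and no rationale. It does not say whether the Time Zero value or some summary of day 0 is used. The Time Zero value is the natural reading, and it lies below 1.7 mg/dL by construction.

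Three of the other subgroups have numeric cuts: "Renal Function: Creatinine ≥ 1.2 vs. < 1.2 mg/dL", SOFA at 8, and "Age: ≥ 65 vs. < 65 years". The fourth, vasopressor use, is yes/no. Magnesium is the only subgroup whose boundary comes from the data. On inference the section adds: "Interaction p-values between subgroups will be estimated via bootstrap-based covariance correction".

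**The concern.** The protocol says the study is meant to inform guidance on whether routine magnesium repletion is needed and safe. For that purpose it matters whether the effect depends on how low magnesium is. This subgroup is the only stated analysis that addresses the question, since the only treatment interaction named in SAP section 3 is with SOFA.

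A reader will take 'Severe' as a clinical category. What the plan produces is the lower part of one sample, all of it already below the entry limit. An absent interaction could be read as no dependence on severity, although the two groups may differ little in magnesium. A present one could be read as a finding about severe disease, although the plan never says what level that is. Without a mg/dL value, the cut cannot be applied in another cohort either.

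**Working it through.** **No figure to reproduce.** The documents give no sample size, magnesium distribution, median or reporting precision. What follows from definitions comes first; the rest is illustration under stated assumptions.

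**Step 1: what follows without assumptions.** For any sample median m, the share below m is at most 50% and the share at or below m is at least 50%. The lower group is therefore nominally half of any cohort, with or without an entry limit. The limit of 1.7 mg/dL does something else: it bounds the upper group from above and so narrows the possible contrast.

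**Step 2: contrast between groups, continuous values.** Assume magnesium is Normal with mean 1.7, 1.8, 1.9, 2.0 or 2.1 and SD 0.2, 0.3 or 0.4 mg/dL, truncated below 1.7 (15 combinations, simulated) and split at the median. Three of the combinations:

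| Mean, SD | Median | Mean of lower group | Mean of upper group | Difference |
|---|---|---|---|---|
| 2.1, 0.2 | 1.64 | 1.58 | 1.67 | 0.09 |
| 1.9, 0.3 | 1.56 | 1.41 | 1.63 | 0.22 |
| 1.7, 0.4 | 1.43 | 1.19 | 1.57 | 0.38 |

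The first and last rows are the extremes of the 15. The share of the lower group at 1.4 mg/dL or above, that is within 1.7 - 1.4 = 0.3 of the entry limit, runs from 9.4% (mean 1.7, SD 0.4) to 98.0% (mean 2.1, SD 0.2). The same label could therefore describe very different patients.

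**Step 3: ties, values rounded to 0.1 mg/dL.** The highest admissible value is then 1.6. Lower-group share under the two possible tie rules:

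| Mean, SD | Median | Lower group if < median | Lower group if <= median |
|---|---|---|---|
| 2.1, 0.3 | 1.5 | 22.7% | 50.0% |
| 1.9, 0.3 | 1.5 | 33.1% | 60.2% |
| 1.7, 0.4 | 1.4 | 42.3% | 59.0% |
| 1.9, 0.4 | 1.5 | 49.0% | 71.8% |
| 2.1, 0.2 | 1.6 | 24.5% | 100.0% |

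Over all 15 combinations the lower group is about 23% to 49% under '<' and 50% to 100% under '<='. It reaches 100% in the four combinations where the median is 1.6 (SD 0.2, mean 1.8 to 2.1), which leaves the upper group empty.

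**Step 4: a check by hand.** Assume these shares at 1.6 / 1.5 / 1.4 / 1.3 / 1.2 or less, and add up from the bottom.

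- 35/25/15/10/15%: 15 + 10 + 15 = 40% below 1.5, and 40 + 25 = 65% at or below. Median 1.5; lower group 40% or 65%.
- 45/25/12/8/10%: 10 + 8 + 12 = 30% below 1.5, and 30 + 25 = 55% at or below. Median 1.5; lower group 30% or 55%.
- 55/20/10/7/8%: 8 + 7 + 10 + 20 = 45% below 1.6, and 45 + 55 = 100% at or below. Median 1.6; lower group 45% or 100%.

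**Step 5: direction.** In every simulated case with two non-empty groups, the lower group had the lower mean magnesium. The split orders patients correctly; what it loses is the variation within each group.

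**The case against.** A median split is mechanical and blind to outcome. It leaves no discretion over the cut, and without heavy ties it gives groups of similar size. Reporting the median in mg/dL would let readers judge the contrast for themselves. This is also one of five subgroup analyses and touches no primary or secondary outcome. All of that stands, and it limits the weight of the point.

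Several stronger readings are tempting, and the documents do not support them:

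- *The split does not measure severity.* It ranks patients by magnesium, so it captures relative depth, coarsely.
- *The entry limit is why about half are called 'Severe'.* A median split does that in any cohort; the limit only narrows the range.
- *Values cluster just under 1.7.* No distribution is given, and the first value below the limit may already be far below it.
- *The cut moves between bootstrap resamples.* The SAP does not say so. Calling these baseline subgroups fits classifying each patient once.
- *A group will be empty.* That arises only under particular assumed distributions and one tie rule, and an analyst would notice it.

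It is also fair to say that a new fixed cut-point chosen now, in a study listed as completed, could not readily be shown to be blind to results. That is a reason to prefer a continuous analysis to a different dichotomy.

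**Conclusion.** The point holds in a limited form. On the documents alone, the plan cuts an already restricted variable at an unstated sample median and calls the parts 'Severe' and 'Mild' without defining severity anywhere. It gives no tie rule and does not say which magnesium value is classified. The result would be a coarse comparison of relative depth under a label that suggests a clinical threshold.

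The sizes in the working (mean difference 0.09 to 0.38 mg/dL; lower group 23% to 49% or 50% to 100% depending on the tie rule) rest on assumed distributions and, for the ties, on assumed 0.1 mg/dL reporting. They show what could happen and do not predict this cohort. The labelling defect and the loss of information do not depend on them. The overall risk differences and risk ratios are unaffected, so this is an improvement worth making to one subgroup analysis and does not threaten the main result.

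**What to change.** In SAP section 5 item 1:

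1. Make the main severity analysis a treatment-by-baseline-magnesium term, using the Time Zero value as a continuous variable. Baseline magnesium is not among the baseline covariates in SAP section 2, so add it there for this analysis. State the functional form; the plan already uses quadratic terms for continuous variables.
2. Report the risk difference between strategies, with bootstrap confidence intervals, at stated magnesium values across the observed range. Say whether the other baseline covariates are averaged over the whole cohort or over patients near each value.
3. If the median split is kept as a display, call the groups below and above median and drop 'Severe' and 'Mild'. Give the median in mg/dL and the tie rule, and hold the cut fixed across resamples.
4. Protocol section 2 lists the study as completed. If results have been seen, label the continuous analysis post hoc. The relabelling and the reporting of the median and tie rule can still be done at the write-up.

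The cost is extra conditional g-formula simulation within the bootstrap, plus an assumption about the shape of the interaction. Estimates at the lowest magnesium values may be imprecise if few patients are there. Item 3 alone costs only wording.

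### Renal replacement therapy is neither excluded nor recorded, leaving a potential time-varying confounder that creatinine, CCI and SOFA capture only in part

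*Combined protocol and SAP*

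**What the plan says.** **Who enters.** Section 1, item 6 (Eligibility Criteria) admits adult ICU patients who meet "Developed hypomagnesemia (Serum Magnesium < 1.7 mg/dL) within the first 72 hours of ICU admission". The three exclusions are "Admitted due to cardiac or cardiosurgical causes (e.g., Cardiac Surgery Recovery Unit, CCU, CVICU", "Underwent cardiac surgery during hospitalization (identified by ICD-9/10 procedure codes" and "Primary discharge diagnosis of major cardiac conditions (e.g., myocardial infarction, heart failure, arrhythmias". None concerns the kidney.

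**What is measured.** Section 2, item 2 (Variables) lists age, gender and CCI at baseline. The daily laboratory covariates are "Laboratory: Serum magnesium, Hemoglobin, Creatinine, Arterial pH". Mean blood pressure, SOFA and vasopressor use complete the daily set, and vasopressor use is the only therapeutic. The exposure is "Magnesium replacement therapy (binary variable per day: administered yes/no".

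**What is modelled.** Section 2, item 3, Step 1 fits models for death, live discharge and seven covariates: Mg, Hb, Cr, pH, MBP, SOFA and vasopressors. These carry lagged values, cumulative averages and quadratic terms, plus a treatment-by-SOFA interaction.

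**What is checked.** Section 2, item 4 has three sensitivity analyses: dropping the quadratic terms, dropping the interaction, and an E-value. Section 2, item 5 says "Treatment effects will be evaluated across the following baseline subgroups", and the renal one is "Renal Function: Creatinine ≥ 1.2 vs. < 1.2 mg/dL".

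**The concern.** The parametric g-formula identifies the strategy contrasts only if the measured history on each day accounts for the joint causes of magnesium treatment and later death. RRT is a plausible joint cause. It marks severe illness, and it is likely to influence whether magnesium is given. It also acts directly on three of the modelled laboratory values: creatinine, pH and serum magnesium.

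Two features of this plan make that more than a routine missing covariate.

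- On RRT days creatinine reflects the circuit as well as the kidney, so its relation to later magnesium, later creatinine and death may differ from that on other days. Nothing in the model specification allows for the difference.
- Serum magnesium defines entry, triggers the Dynamic Treat rule and is itself simulated forward. RRT can move it without any entry in the yes/no treatment flag.

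At stake is whether part of any difference between Always, Dynamic and Never Treat comes from which days were RRT days. A secondary matter is what the creatinine-based renal subgroup represents when RRT patients are in it.

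**Working it through.** **Step 1. Is there a figure to reproduce?** No. The plan states no sample size, event count, power, RRT prevalence or treatment rate. The premise was checked by reading every list in which RRT could appear.

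| Place | Does RRT or end-stage kidney disease appear? |
|---|---|
| Inclusion and exclusion criteria | No; all three exclusions are cardiac |
| Baseline covariates | No; CCI is a composite |
| Daily covariates | No; vasopressor is the only therapy |
| Step 1 models | No; seven covariates, none of them RRT |
| Competing event | No; live discharge only |
| Sensitivity analyses | No; none adds a confounder or removes patients |
| Subgroups | No; creatinine cut only |

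**Step 2. Possible size of the confounding (all inputs assumed).** Let π be the share of patient-days on RRT, t₁ and t₀ the shares of RRT and other days on which magnesium is given, and HR the death hazard ratio for RRT that remains after the adjustment set. The RRT shares among treated and untreated days are

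- p₁ = πt₁ / [πt₁ + (1−π)t₀]
- p₀ = π(1−t₁) / [π(1−t₁) + (1−π)(1−t₀)]

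With no true effect of magnesium, the treated-versus-untreated daily death risk is multiplied by [1+(HR−1)p₁] / [1+(HR−1)p₀].

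Worked case: π = 10%, t₁ = 10%, t₀ = 40%.

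- p₁ = 0.01 / (0.01 + 0.36) = 0.027
- p₀ = 0.09 / (0.09 + 0.54) = 0.143
- With HR = 2.0 the factor is 1.027 / 1.143 = 0.90.

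Other cases, with t₀ = 40% throughout:

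| π | t₁ | HR 1.5 | HR 2.0 |
|---|---|---|---|
| 2% | 10% | 0.99 | 0.98 |
| 5% | 10% | 0.97 | 0.94 |
| 10% | 10% | 0.95 | 0.90 |
| 15% | 10% | 0.92 | 0.86 |
| 10% | 30% | 0.98 | 0.97 |
| any | 40% | 1.00 | 1.00 |
| 5% | 60% | 1.02 | 1.04 |
| 15% | 60% | 1.05 | 1.09 |

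The range is 0.86 to 1.09, and the sign depends on whether RRT patients receive magnesium less or more often than others. The relevant gap between t₁ and t₀ is the one left after magnesium, creatinine and SOFA are adjusted for. The 10% against 40% rows are therefore towards the extreme, and the 30% against 40% row may be nearer to what remains.

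**Step 3. The renal subgroup (all inputs assumed).** Let r be the share of patients on RRT at baseline, m the share of those with creatinine below 1.2 mg/dL, and take 60% of other patients as below 1.2.

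- RRT share of the < 1.2 stratum: rm / [rm + (1−r)0.6]
- RRT share of the ≥ 1.2 stratum: r(1−m) / [r(1−m) + (1−r)0.4]

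For r = 2–10% and m = 5–40%:

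- Lower stratum: from 0.2% (r = 2%, m = 5%: 0.001/0.589) to 7% (r = 10%, m = 40%: 0.04/0.58).
- Upper stratum: from 3% (r = 2%, m = 40%: 0.012/0.404) to 21% (r = 10%, m = 5%: 0.095/0.455).

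On these inputs the main effect is a mixed upper stratum.

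**The case against.** The other side has four good arguments.

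1. **The models are richer than a single creatinine term.** A patient whose creatinine has just fallen from a high value keeps a high lagged and cumulative-average creatinine, so the models can partly separate that patient from one who was always low. A reader might infer that every fall in creatinine on RRT is treated as renal recovery under one coefficient; the specification in Section 2, item 3 does not support that. What survives is that these terms do not identify RRT days, and that a fall from any other cause leaves the same trace.

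2. **Other variables carry renal information.** CCI and SOFA, as usually defined, do so, and pH and magnesium are modelled daily. This reduces the residual confounding, but composites and laboratory values do not say who is on RRT.

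3. **The subgroup is defined at baseline.** A reader might infer that the < 1.2 stratum is filled with the sickest kidneys. Only patients already on RRT and already cleared below 1.2 at baseline would be placed there, which Step 3 puts at 7% of that stratum at most. Nor does the plan make this subgroup its safety analysis: the safety aim in Section 1, item 3 is general, and no safety outcome is listed.

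4. **The E-value is prespecified for unmeasured confounding.** It says how strong a confounder would have to be. It does not adjust for one that could be recorded, and it does nothing for a covariate whose meaning changes on RRT days.

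It is also true that the size rests wholly on assumptions and may be close to nil. That argues for measuring RRT, because without the variable a reader cannot tell which row of the table applies.

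**Conclusion.** The point stands as a gap in the adjustment set that should be closed. RRT is an unrecorded potential time-varying confounder in an analysis that depends on measuring such confounders.

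It may bias the contrasts between strategies. A reader might go further and conclude that it does bias all three simulated strategies, or that the bias favours treatment. The documents support neither, since the direction is open and the bias vanishes if RRT shares are equal on treated and untreated days.

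The factor of about 0.86 to 1.09 rests on assumed prevalence (2–15%), residual hazard ratio (1.5–2.0) and treatment rates (10–60% against 40%). It applies to daily death risk and has not been carried through to the 28-day risk ratio or risk difference. It should not be applied uniformly to every contrast either: Dynamic and Never Treat assign different treatment only on days with magnesium below 1.7 mg/dL.

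The renal subgroup is the lesser part: RRT patients mainly mix the ≥ 1.2 stratum, and a few cleared below 1.2 are labelled as having better function.

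**What to change.** **Change.**

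- In Section 2, item 2, add a daily RRT yes/no variable to the time-varying covariates, of the same kind as the vasopressor flag.
- In Section 2, item 3, Step 1, give it its own model and include it in the Mg, Cr, death and discharge models.
- In Section 2, item 4, add a sensitivity analysis, for the main result and the renal subgroup, that excludes patients with end-stage kidney disease or RRT before Time Zero. Restrict the exclusion to status before Time Zero: removing patients who start RRT later would select on follow-up events.
- Report the proportion of patient-days on RRT, split by magnesium treatment, so that readers can judge the size for themselves.
- State as a limitation that magnesium delivered through RRT fluids stays outside the yes/no exposure. The indicator does not repair this.

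**Optional.** An RRT-by-creatinine term, and a third renal stratum for patients on RRT or with end-stage kidney disease at Time Zero. The third stratum may be small, with a wide interval.

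**Cost.** SAP wording, one more binary covariate model, a re-run on existing data and slightly wider intervals, assuming that RRT can be extracted from the database by day. Section 1, item 2 gives the study as completed, so the added analyses should be dated and labelled as additions to the plan.

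### Five subgroup interaction p-values are read at an unadjusted 0.05, with no contrast, scale, multiplicity rule or exploratory label stated

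*Combined protocol and SAP*

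**What the plan says.** SAP section 5 names five baseline factors: hypomagnesemia severity (split at the median), creatinine, vasopressor use, SOFA and age. It then states: "Interaction p-values between subgroups will be estimated via bootstrap-based covariance correction". It does not say which contrast is examined or on which scale.

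SAP section 6, under Software, gives the only decision rule: "A two-sided p-value < 0.05 will be considered statistically significant". There is no multiplicity procedure, hierarchy or exploratory label anywhere in the plan.

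SAP section 3, Step 3, compares Always Treat and Dynamic Treat with Never Treat, each by RD and RR, with bootstrap 95% CIs. Neither contrast and neither scale is given priority. Protocol section 7 names one primary outcome, 28-day mortality. It lists RD as a secondary outcome, defined as "The absolute difference in mortality risk between the emulated strategies (Never/Always/Dynamic) and the natural clinical course or between strategies". RR is not in the outcome list. Protocol section 5 gives the natural clinical course as the reference, whereas SAP section 3 uses Never Treat.

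The document is dated December 24, 2025 and the study status is Completed. Protocol section 2 gives the start as September 2025 and describes it as the start of analysis.

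**The concern.** A single 0.05 threshold applied to several interaction p-values does not hold the chance of a false subgroup claim at 5%. The study says it aims to inform clinical guidelines, and an apparent effect confined to a renal, vasopressor or SOFA subgroup is the kind of result that readers carry into practice.

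The unstated scale adds a second problem. Subgroups defined by SOFA or age can be expected to differ in baseline mortality. When they do, effect modification on RD and effect modification on RR are different hypotheses and can give opposite answers. If the scale is left open, it can be chosen after both answers are known.

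**Working it through.** **Inputs from the documents.** Two-sided level 0.05 (SAP 6); five subgroup factors (SAP 5); two main contrasts, each by RD and RR (SAP 3, Step 3). The plan gives no family-wise error rate, event count or power, so it has no figure of its own to reproduce.

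**Assumed inputs.** No true effect or interaction anywhere (the global null); each test has an exact 5% error rate on its own; correlation a between the two contrasts, from 0 to 1 (they share the Never Treat reference and the fitted models); correlation b between subgroup factors, from 0 to 0.5.

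**Step 1: independent tests.** P(at least one p < 0.05) = 1 - 0.95^m.
- m = 2: 1 - 0.95^2 = 9.75%
- m = 5: 1 - 0.95^5 = 22.6%
- m = 10: 1 - 0.95^10 = 40.1%

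**Step 2: correlated interaction tests.** Simulated two-sided z-tests, 1,000,000 draws per setting, five factors by two contrasts. Chance of at least one p < 0.05:

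| a (contrasts) | b = 0 | b = 0.2 | b = 0.5 |
|---|---|---|---|
| 0 | 40.2% | 38.8% | 33.3% |
| 0.5 | 37.9% | 36.7% | 31.1% |
| 0.8 | 33.4% | 32.2% | 27.1% |
| 0.95 | 28.4% | 27.3% | 22.8% |
| 1 | 22.7% | 21.9% | 18.3% |

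The top-left cell agrees with the exact 40.1% within simulation error. With a = 1 the two contrasts give the same test, so the last row is also the result for one contrast with five tests: about 18-23%. The whole table gives about 18-40% for ten tests.

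**Step 3: the two main contrasts.** 9.75% if independent, then 9.1%, 7.8%, 6.5% and 5.0% at a = 0.5, 0.8, 0.95 and 1. Reporting both RD and RR does not double this, because R1 - R0 = 0 exactly when R1/R0 = 1: the two scales share one null.

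**Step 4: scale of the interaction.** With baseline risk p and a common RR, RD = p × (RR - 1). At an assumed RR of 0.9:
- p = 40%: RD = 40 × (-0.1) = -4 points
- p = 10%: RD = 10 × (-0.1) = -1 point

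The RDs differ by 3 points, while the ratio of the RRs is 0.9/0.9 = 1. In general the RD gap is 0.1 × (difference in baseline risk): 0 points if the baseline risks are equal, 1 point if they differ by 10 points, 2 if by 20, and 3 if by 30. The documents give no subgroup risks, so these are illustrations only.

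**Step 5: effect of Holm adjustment.** The smallest p-value is compared with 0.05/5 = 0.01 for five tests, or 0.05/10 = 0.005 for ten. Under the global null with independent tests, the chance of any false claim is 1 - 0.99^5 = 4.9%, or 1 - 0.995^10 = 4.9%.

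**The case against.** The strongest reply is that this is an observational emulation aimed at estimation. It has one primary outcome, and its main results are planned as estimates with 95% CIs. The five factors are listed, four with explicit splits and one at the median. Whether two related contrasts need adjustment in such a study is debatable. That stands for the main contrasts, where the inflation is at most from 5% to 9.75%. It does not answer the subgroup point, because the plan itself schedules interaction p-values and declares a threshold that covers them.

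The covariance correction in SAP 5 might be taken as a multiplicity adjustment. As written, it describes how each p-value is estimated, and nothing makes it an adjustment across tests. Because it is not defined further, the 5% error rate per test remains an assumption.

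A reader might also infer four stronger things:

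- **That a false positive is likely.** Even counting two main contrasts and ten interactions together, the chance is 1 - 0.95^12 = 46.0% if all are independent, and about 22% at the high-correlation end. That is substantial but below even odds.
- **That two scales double the main tests.** They do not, for the reason in Step 3.
- **That five interactions are planned for each contrast.** The plan does not say so. With one contrast, the figure is at most 22.6%.
- **That the late date shows choices made after seeing results.** The date removes assurance of prior specification. It does not change the error rates above, and the documents do not show whether an earlier version existed.

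**Conclusion.** The concern holds for the subgroup interactions. Under the plan as written, the chance of at least one falsely significant interaction is about 18-23% with one contrast and about 18-40% with both, against the nominal 5%. The upper end needs independence between contrasts that share a reference arm and models, so it is a bound rather than an expectation. The figures rest on the assumed correlations and on each test having its nominal size.

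The missing scale is a separate and real gap, because RD and RR can disagree about whether an interaction exists.

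For the main contrasts the inflation is modest (5.0-9.75%). Naming a primary contrast or fixed test order now would not cure it: that protects the error rate only if it is set before results are seen, and this plan is dated after analysis began. If contrasts with the natural course are also tested, as the protocol's RD definition permits, the family is larger than counted here.

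**What to change.** - **SAP 5, scale and contrast.** State that interactions are tested on the RD scale, which the protocol already lists as an outcome. Show the RR-scale result alongside without a significance claim. State whether one contrast or both are tested.
- **SAP 6, threshold.** Limit the 0.05 rule so that a subgroup interaction is called significant only after Holm adjustment across the five factors, or across all ten tests if both contrasts are tested. Otherwise report subgroup estimates with 95% CIs, labelled exploratory, with no significance statement.
- **Main contrasts.** Report Always versus Never and Dynamic versus Never together, with equal prominence. Do not name a primary contrast or fixed sequence now.
- **Report.** Say that the plan is dated December 24, 2025, after the September 2025 analysis start, and that the documents do not show that contrasts, scale and cut-points were fixed before results were seen.

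The cost is SAP wording, less favourable interaction p-values and lower power to declare an interaction. No new data or models are needed. Holm adjustment covers the number of tests; it cannot undo a choice of scale or cut-point made after seeing results, which is why the RR results and the disclosure are part of the fix.
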